 - Criterion 4a is applicable only to enrollment of melanoma subjects in Parts 1, 2, and 3 of the trial design. Criterion 4b is applicable only to enrollment of melanoma subjects in Parts 1, 2, 4, and 5 of the trial design. The inclusion criterion does not apply to solid tumor subjects in Parts 4 and 5 (dose confirmation only).

Note: Local laboratory testing for BRAF mutation is acceptable provided the methodology can detect both V600E and V600K mutations.

5. For BRAF mutation-negative (wild type) subjects who have received prior therapy for metastatic or advanced melanoma, must have documented progression of at least one measurable lesion by RECIST 1.1 on imaging studies (CT or MRI).
6. Have a performance status of 0 or 1 on the Eastern Cooperative Oncology Group (ECOG) Performance Scale.
7. Have an anticipated life expectancy of at least 3 months.
8. Be able to swallow and retain oral medication and must not have any clinically significant gastrointestinal abnormalities that may alter absorption such as malabsorption syndrome or major resection of the stomach or bowels.

9. Have adequate organ function as defined in [Table 8](#) below:

Table 8 Inclusion Criteria Laboratory Parameters

System	Laboratory Value
Hematological	
Absolute neutrophil count (ANC)	≥1,500 /mcL
Platelets	≥100,000 / mcL
Hemoglobin	≥9 g/dL or ≥5.6 mmol/L
Renal	
Serum creatinine	≤1.5 X upper limit of normal (ULN)
Calculated creatinine clearance ^a	≥50 mL/min
Hepatic	
Serum total bilirubin	≤ 1.5 X ULN OR Direct bilirubin ≤ ULN for subjects with total bilirubin levels > 1.5 X ULN
AST (SGOT) and ALT (SGPT)	≤ 2.5 X ULN
Alkaline Phosphatase	If > 2.5 X ULN, then liver fraction should be ≤ 2.5 X ULN
Albumin	≥ 2.5 g/dL
Coagulation	
International Normalized Ratio (INR) or Prothrombin Time (PT)	≤1.5 X ULN unless the subject is receiving anticoagulant therapy as long as PT or aPTT is within therapeutic range of intended use of anticoagulants
Activated Partial Thromboplastin Time (aPTT)	≤1.5 X ULN unless the subject is receiving anticoagulant therapy as long as PT or aPTT is within therapeutic range of intended use of anticoagulants
a Calculate creatinine clearance using standard Cockcroft-Gault formula (Appendix 12.7). Creatinine clearance must be ≥50 mL/min to be eligible.	

10. Have provided tissue for biomarker analysis from a newly or recently-obtained biopsy (within 90 days of Study Day 1) of a tumor lesion not previously irradiated.

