5.2.4.3 Dose Limiting Toxicity

Toxicities will be graded using National Cancer Institute (NCI) CTCAE Version 4.0. A DLT evaluable subject is defined as a subject who receives treatment for the 6-week dose-limiting toxicity (DLT) observation period and who receives at least 66% of all planned treatments. A subject who does not receive at least 66% of planned treatment due to AEs that are unrelated to study treatment will not be considered evaluable for DLTs and may be replaced as needed during dose escalation or dose confirmation. More than 3 or 6 subjects may be enrolled to a given dose level if needed to replace subjects who are not evaluable for DLT or to ensure a thorough evaluation of a given dose level during the dose escalation part of the study. An event will be considered a dose-limiting toxicity (DLT) if it occurs during the first cycle of treatment in dose identification and confirmation subjects (first 6 weeks after initiating pembrolizumab treatment) and meets at least one of the following criteria:

- Clinically significant hematologic toxicity (e.g. grade 4 neutropenia lasting more than 7 days or accompanied by neutropenic fever, or Grade 4 thrombocytopenia of any duration)
- Clinically significant Grade ≥ 3 non-hematologic toxicity that has not been previously identified for either pembrolizumab or dabrafenib/trametinib and cannot be controlled with routine supportive measures (e.g. anti-emetics)
- Clinically significant Grade ≥ 3 non-hematologic toxicities that are known to occur with either pembrolizumab or dabrafenib/trametinib but that cannot be controlled using the recommended product-specific supportive measures (e.g. steroids for pembrolizumab-related immune toxicities)
- Drug-related toxicity, regardless of CTCAE grade, that results in an interruption of any component of study therapy during Cycle 1 for more than 21 consecutive days and cannot be controlled within 2 weeks from its onset
- Any other Grade 2 or greater non-hematological toxicity that in the judgment of the investigator and Sponsor is dose limiting, with the exception of mild or moderate immune-mediated adverse reactions or symptomatic endocrinopathy attributable to pembrolizumab
- Liver chemistries meeting stopping guidelines (as outlined in Section 5.6.1.1.15):
 1. ALT or AST ≥ 3 xULN and bilirubin ≥ 2 xULN (>35% direct bilirubin) (or ALT/AST ≥ 3 xULN and INR >1.5, if INR measured)

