5.5.1 Acceptable Concomitant Medications

All treatments that the investigator considers necessary for a subject's welfare may be administered at the discretion of the investigator in keeping with the community standards of medical care. All concomitant medication will be recorded on the case report form (CRF) including all prescription, over-the-counter (OTC), herbal supplements, and IV medications and fluids. If changes occur during the trial period, documentation of drug dosage, frequency, route, and date may also be included on the CRF.

Use of anticoagulants such as warfarin is permitted; however, caution should be exercised and additional International Normalized Ratio (INR) monitoring is recommended when dabrafenib is used concomitantly with warfarin. See Section 5.5.3 Medications to be Used with Caution.

All concomitant medications received within 28 days before the first dose of trial treatment and 30 days after the last dose of trial treatment should be recorded. Concomitant medications administered after 90 days after the last dose of trial treatment should be recorded for SAEs and ECIs as defined in Section 7.2.

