5.5.3 Medications to be Used with Caution

The following medications should be used with caution during the Screening and Treatment Phases of this trial, as their concentrations may be altered by dabrafenib or they may alter dabrafenib concentrations:

- Drugs that are moderate inhibitors or inducers of CYP3A and CYP2C8 as they may alter concentrations of dabrafenib.
- Dabrafenib has been shown to induce CYP3A4 and CYP2C9 in vivo using midazolam (CYP3A4 substrate) and S-warfarin (CYP2C9 substrate). Dabrafenib is an in vitro inducer of CYP2B6 and other enzymes such as CYP2C8, CYP2C19, UDP-glucuronyl transferases. Transporters may also be affected. Co-administration of dabrafenib and medications which are affected by the induction of these enzymes (including warfarin) and transporters may result in loss of efficacy. If co-administration of these medications is necessary, investigators should monitor subjects for loss of efficacy or consider substitutions of these medications. A partial list of these medications is provided in [Table 15](#).
- Therapeutic level dosing of warfarin can be used with approval by the medical monitor and close monitoring of PT/INR by the site. Warfarin exposure has been shown to decrease (37% decrease) due to dabrafenib-mediated enzyme induction. Conversely, if dabrafenib dosing is reduced, interrupted, or discontinued, warfarin exposure may be increased. Thus, warfarin dosing may need to be adjusted based on PT/INR during and after treatment with dabrafenib. Prophylactic low dose warfarin may be given to maintain central catheter patency.
- Dabrafenib solubility is pH-dependent with decreased solubility at higher pH. Drugs such as proton pump inhibitors that inhibit gastric acid secretion to elevate gastric pH may decrease the solubility of dabrafenib and reduce its bioavailability. No clinical study has been conducted to evaluate the effect of pH on dabrafenib pharmacokinetics. In an ad-hoc analysis, no differences in C_{max} and AUC were noted between subjects who reported taking pH-elevating products relative to other subjects. Due to the theoretical risk that pH-elevating agents may decrease oral bioavailability and exposure to dabrafenib, these medicinal products that increase gastric pH should be used with caution when administered with dabrafenib.

Table 15 Medications to be used with Caution

USE WITH CAUTION: Moderate inhibitors of CYP3A, or CYP2C8 since concentrations of dabrafenib may be increased	

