AST or ALT \geq 5.0x ULN	
 • Monitor hepatic laboratory tests more frequently until returned to baseline values (consider weekly) • For Grade 2 AST, ALT, or bilirubin elevations, treat with 0.5-1 mg/kg/day methylprednisolone or oral equivalent and when LFT returns to grade 1 or baseline, taper steroids over at least 1 month, consider prophylactic antibiotics for opportunistic infections 	
 • Hold pembrolizumab when AST or ALT $>$3.0x to 5.0x ULN and/or total bilirubin $>$1.5x to 3.0x ULN • Resume pembrolizumab when LFT returns to \leqGrade 1 or baseline • Permanently discontinue pembrolizumab for patients with liver metastasis who begin treatment with Grade 2 elevation of AST or ALT, and AST or ALT increases \geq50% relative to baseline and lasts \geq1 week

Event	Adverse Event Management	Action and Dose Modification

AST or ALT >5.0xULN to ≤8.0xULN without bilirubin elevation (defined as total bilirubin^a ≤2.0xULN, or direct bilirubin ≤35%)
	
 • Consider appropriate consultation and liver biopsy to establish etiology of hepatic injury, if necessary • Treat with high-dose intravenous glucocorticosteroids for 24 to 48 hours. When symptoms improve to Grade 1 or less, a steroid taper with dexamethasone 4 mg every 4 hours or prednisone at 1 to 2 mg/kg should be started and continued over no less than 4 weeks. • If serum transaminase levels do not decrease 48 hours after initiation of systemic steroids, oral mycophenolate mofetil 500 mg every 12 hours may be given. Infliximab is not recommended due to its potential for hepatotoxicity. • Several courses of steroid tapering may be necessary as symptoms may worsen when the steroid dose is decreased. 	
 • Discontinue pembrolizumab if AST/ALT >5.0x ULN and/or total bilirubin >3.0xULN • Hold dabrafenib, and/or trametinib if (any criteria are met): 
 - AST/ALT >5.0x ULN - AST/ALT >3x ULN AND total bilirubin >2x ULN - Total bilirubin > 3x ULN • Interrupt dabrafenib and/or trametinib until recovery to Grade ≤1 • After consultation with Sponsor, dabrafenib and/or trametinib may be restarted reduced by one dose level • If no recovery to grade ≤1 within 2 weeks, permanently discontinue study treatment

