
AST or ALT >3.0 x ULN with concomitant elevation in bilirubin (defined as total bilirubin^a ≥2.0 x ULN with direct bilirubin >35%) OR meeting any liver chemistry stopping criteria (see 5.6.1.1.15.1)
	
 • Same as grade 3 	
 • Permanently discontinue all study treatment

Abbreviations: CTCAE = Common Terminology Criteria for Adverse Events a. Serum bilirubin fractionation should be performed if testing is available. If testing is unavailable and a subject meets the criterion of total bilirubin flix ULN, then the event should be promptly reported as an SAE.
		

Note: in the event of a drug-induced liver injury (DILI) adverse event (as outlined in the study protocol), please follow the DILI guidance outlined in the site Administrative Binder.

5.6.1.1.15.1 Liver Chemistry Stopping Criteria

These liver chemistry stopping and follow-up criteria have been designed to assure subject safety and evaluate liver event etiology in alignment with the FDA Guidance for Industry – Drug-Induced Liver Injury: Premarketing Clinical Evaluation (July 2009, www.fda.gov).

Liver chemistry stopping criteria 1-5 are defined as:

1. AST/ALT ≥3xULN and bilirubin ≥2xULN (>35% direct bilirubin) (or AST/ALT≥3xULN and INR>1.5, if INR measured)

NOTE: If serum bilirubin fractionation is not immediately available, study treatment should be discontinued if $AST/ALT \geq 3xULN$ and bilirubin $\geq 2xULN$. Serum bilirubin fractionation should be performed if testing is available. If testing is unavailable, record presence of detectable urinary bilirubin on dipstick, indicating direct bilirubin elevations and suggesting liver injury.

2. $AST/ALT \geq 8xULN$
3. $AST/ALT \geq 5xULN$ but $<8 xULN$ persists for ≥ 2 weeks
4. $AST/ALT \geq 3xULN$ if associated with the appearance or worsening of symptoms of hepatitis or hypersensitivity such as fatigue, nausea, vomiting, right upper quadrant pain or tenderness, pyrexia, rash or eosinophilia.
5. $AST/ALT \geq 5xULN$ but $<8 xULN$ and cannot be monitored weekly for >2 weeks.

When any of the liver chemistry stopping criteria 1 - 5 is met, do the following:

- **Immediately discontinue subject from** study treatment
- Report the event to Sponsor **within 24 hours** of learning its occurrence
- Complete the liver event CRF and SAE data collection tool if the event also meets the criteria for an SAE

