 - All events of $ALT \geq 3xULN$ **and** bilirubin $\geq 2xULN$ ($>35\%$ direct bilirubin) (or $ALT \geq 3xULN$ and $INR > 1.5$, if INR measured; INR measurement is not required and the threshold value stated will not apply to subjects receiving anticoagulants), termed 'Hy's Law', **must be reported as an SAE**.
 - NOTE: if serum bilirubin fractionation is not immediately available, study treatment should be discontinued if $ALT \geq 3xULN$ **and** bilirubin $\geq 2xULN$. Serum bilirubin fractionation should be performed if testing is available. If testing is unavailable, **record presence of detectable urinary bilirubin on dipstick**, indicating direct bilirubin elevations and suggesting liver injury
- Complete the liver imaging and/or liver biopsy CRFs if these tests are performed
- Perform liver event follow up assessments, and monitor the subject until liver chemistries resolve, stabilize, or return to baseline values as described below
- Follow up for overall survival is required following discontinuation from study treatment.
- Do not rechallenge with study treatment.

In addition, for subjects meeting liver stopping criterion 1:

- Make every reasonable attempt to have subjects return to clinic **within 24 hours** for repeat liver chemistries, liver event follow up assessments, and close monitoring
- A specialist or hepatology consultation is recommended
- Monitor subjects twice weekly until liver chemistries (ALT, AST, alkaline phosphatase, bilirubin) resolve, stabilize or return to within baseline values.

For subjects meeting any of the liver stopping criteria 2 – 5:

- Make every reasonable attempt to have subjects return to clinic **within 24-72 hrs** for repeat liver chemistries and liver event follow up assessments
- Monitor subjects weekly until liver chemistries (ALT, AST, alkaline phosphatase, bilirubin) resolve, stabilize or return to within baseline values;
- Subjects meeting criterion 5 should be monitored as frequently as possible.

5.6.1.1.15.2 Liver Event Follow-up Assessments

For subjects meeting any of the liver chemistry stopping criteria 1 – 5, make every attempt to carry out the **liver event follow up assessments** described below:

- Viral hepatitis serology including:
 - Hepatitis A IgM antibody
 - Hepatitis B surface antigen and Hepatitis B Core Antibody (IgM)
 - Hepatitis C RNA
 - Cytomegalovirus IgM antibody

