- 9 Routine laboratory tests (chemistry; hematology) for screening should be performed within 10 days prior to the first dose of trial treatment. See Section 7.1.3 for details regarding laboratory tests.
- 10 For women of reproductive potential, a urine pregnancy test will be performed within 72 hours prior to first dose of trial treatment. If urine pregnancy results cannot be confirmed as negative, a serum pregnancy test, performed by the local study site laboratory, will be required. Pregnancy tests (serum and/or urine tests) should be repeated if required by local guidelines.
- 11 After Cycle 1, lab samples can be collected up to 48 hours prior to the scheduled time point. Laboratory results must be known and acceptable prior to dosing. See Section 7.1.3 for details regarding laboratory tests.
- 12 Coagulation factors (PT/INR and aPTT) should be monitored closely throughout the trial for any subject receiving anticoagulant therapy.
- 13 Thyroid function tests will be performed by a central laboratory only if the local laboratory is unable to perform this service. Following Cycle 4, testing will be performed every other cycle. In countries where T3 results are not available, FT3 results may be reported. See Section 7.1.3 for details regarding laboratory tests.
- 14 Testing will be performed by the local laboratory at Screening. Hepatitis B and Hepatitis C serologies should be obtained for subjects without a known history of Hepatitis B or C. Those with a known history are ineligible. Include HCV RNA (qualitative) and HBsAg.
- 15 Informed consent for Future Biomedical Research (FBR) samples must be obtained before the DNA sample is drawn. DNA sample for analysis should be obtained predose, on Day 1 (or with the next scheduled blood draw), as the last sample drawn, on allocated subjects only, or at a later date as soon as the informed consent is obtained. This sample should only be taken once from each subject. See Section 12.2 for guidance regarding the collection and management of specimens for FBR.

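### Liver stopping criterion 1 and DLT liver item 1 lack the anticoagulant exemption from the INR limb that the same section writes into its Hy's Law reporting bullet

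*Combined protocol and SAP*

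**What the plan says.** Section 5.6.1.1.15.1, criterion 1, stops treatment for AST/ALT of at least 3×ULN with bilirubin of at least 2×ULN or, alternatively, with "INR>1.5, if INR measured". Section 5.2.4.3, liver item 1, makes the same combination a DLT ("INR >1.5, if INR measured") and refers to Section 5.6.1.1.15 for the stopping guidelines.

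The Hy's Law bullet in Section 5.6.1.1.15.1, which governs SAE reporting, repeats the INR limb for ALT and adds: "INR measurement is not required and the threshold value stated will not apply to subjects receiving anticoagulants".

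Elsewhere the protocol expects anticoagulated subjects:
- Section 5.5.1: "Use of anticoagulants such as warfarin is permitted".
- Section 5.5.3: "Therapeutic level dosing of warfarin can be used with approval by the medical monitor and close monitoring of PT/INR by the site".
- Section 5.1.2, Table 8, waives the INR entry limit: "unless the subject is receiving anticoagulant therapy as long as PT or aPTT is within therapeutic range of intended use of anticoagulants".
- Section 6.1.1, footnote 12, repeated in the other treatment-phase flow charts: "Coagulation factors (PT/INR and aPTT) should be monitored closely throughout the trial for any subject receiving anticoagulant therapy".

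When a stopping criterion is met, Table 30 (last row) permanently discontinues all study treatment, and the action list in Section 5.6.1.1.15.1 rules out rechallenge. Sections 5.6.1.1.15.4 and 5.6.1.1.15.5 let the Sponsor approve a restart under stated conditions.

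**The concern.** In a subject on an anticoagulant, an INR above 1.5 may be the intended effect of a permitted drug and then says little about liver function. The protocol accepts this for Hy's Law reporting but does not say so where the consequences are heavier. For these subjects the condition that INR be measured is met because monitoring is required, so the INR limb may already be satisfied before any liver event. ALT/AST of 3×ULN is then enough.

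Two things are at stake: a subject could lose all study drugs for a finding that is otherwise managed by a temporary hold, and a dose level could be charged with a DLT that reflects the anticoagulant.

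**Working it through.** The plan states no figure on this point. The check compares the texts, follows one test case through the rules, and then sizes the effect under assumed frequencies.

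**1. The three texts**

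| Place | Enzyme limb | INR limb | Exempts anticoagulated subjects |
|---|---|---|---|
| 5.6.1.1.15.1, criterion 1 | AST or ALT ≥3×ULN | >1.5 if measured | No |
| 5.2.4.3, liver item 1 | ALT or AST ≥3×ULN | >1.5 if measured | No |
| 5.6.1.1.15.1, Hy's Law SAE bullet | ALT ≥3×ULN | >1.5 if measured | Yes |

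**2. Test case.** Permitted anticoagulant, INR >1.5, ALT/AST between 3 and 5×ULN, no raised bilirubin, no symptoms.
- Criterion 1, bilirubin limb (≥2×ULN): not met.
- Criterion 2 (≥8×ULN): not met.
- Criteria 3 and 5 (≥5×ULN): not met.
- Criterion 4 (≥3×ULN with hepatitis or hypersensitivity symptoms): not met.
- Criterion 1, INR limb: met.

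Only the INR limb fires. The DLT items follow the same pattern. Section 5.2.4.3 excludes clinically insignificant laboratory values from DLTs, but its example is amylase and lipase. It does not name INR and does not touch the stopping rule.

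**3. Handling with and without the INR limb**
- Without it, Table 30 holds pembrolizumab ("For Grade 2 AST, ALT, or bilirubin elevations, treat with 0.5-1 mg/kg/day methylprednisolone or oral equivalent", then a taper of at least one month) and resumes it at Grade 1 or lower, or at baseline. It discontinues pembrolizumab permanently only for liver-metastasis subjects who start at Grade 2 AST/ALT and rise by at least 50% for at least a week. The dabrafenib/trametinib hold rule (AST/ALT >5×ULN; >3×ULN with bilirubin >2×ULN; or bilirubin >3×ULN) is not met.
- With it, the default is a permanent stop of everything and, within 6 weeks of the first pembrolizumab dose, a DLT.

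**4. Size.** The documents give no rate for anticoagulant use or for isolated ALT/AST of 3–5×ULN. Let p be the true DLT rate and f the assumed share of subjects without another DLT who meet only this limb. The counted DLT rate is q = p + (1 − p)f.

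Under a 3+3 rule that rejects at ≥2/3 or ≥3/6, let T = 3q²(1 − q) + q³. The rejection probability is R = T + 3q(1 − q)²·T.

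For p = 0.20 and f = 0: T = 0.1040, 3q(1 − q)² = 0.3840, R = 0.1040 + 0.3840 × 0.1040 = 0.1439.

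For p = 0.20 and f = 0.01: q = 0.208, T = 0.1118, 3q(1 − q)² = 0.3914, R = 0.1556.

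| f (assumed) | R at p = 20% |
|---|---|
| 0 | 14.4% |
| 0.1% | 14.5% |
| 0.25% | 14.7% |
| 0.5% | 15.0% |
| 1% | 15.6% |

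At p = 30%, R goes from 31.1% (f = 0) to 31.3%, 31.5% and 31.8% for f of 0.1%, 0.25% and 0.5%.

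**5. Decision cells one case can move**
- Part 4 (Section 5.2.4.1.2): 2/6 to 3/6 at any level. The step from 1/3 to 2/3 is written only for Dose Levels 1 and -1a.
- Part 5 (Table 13): at the highest S count, one more DLT gives D or DU in every column from n = 3 to 14. It goes straight to DU at n = 4, 6, 9, 11 and 13; for example, 3/6 is S and 4/6 is DU. At n = 14, 6 is S and 7 is D.

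**The case against.** **The exemption may already apply.** It sits in the same section, in the action list for criteria 1–5, and the DLT item defers to Section 5.6.1.1.15. A site could reasonably read it across. This stands as a possible reading, so a reader who infers that the protocol plainly denies the exemption goes too far. But the sentence is attached to a reporting bullet that names ALT only, whereas the stopping and DLT rules name AST as well. A site applying criterion 1 as printed would stop treatment.

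**Stopping first is conservative.** INR cannot separate drug effect from failing synthesis in these subjects, and Section 4.2.1 cites hepatotoxicity with another immunotherapy and MAPK-inhibitor combination. This has some force. However, every bilirubin, enzyme-level and symptom trigger would remain, and Sections 5.6.1.1.15 and 7.2.3.2 already require Grade 2 or higher transaminase elevations to be reported within 24 hours as events of clinical interest.

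**Few subjects qualify.** Criterion 4 already catches cases with fatigue, nausea, vomiting, pyrexia or rash, several of them common with these drugs, and therapeutic warfarin needs approval. This stands and governs the weight of the point.

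**A large loss of dose acceptance might be inferred.** Suppose one affected subject is among the first three at Part 4 Dose Level 1 or -1a and the others have a 30% DLT rate. Acceptance then falls from 0.7² + 2(0.3)(0.7)(0.784) = 81.9% to 0.7² × 0.784 = 38.4%, where 0.784 is the chance of at most one DLT in the next three. That assumes the rare case has happened, and any single extra DLT would do the same. The documents do not support reading it as an average effect.

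**Conclusion.** The wording is inconsistent within one section, and its literal application gives a result the protocol disowns for the same subjects in Hy's Law reporting. The affected set is narrow: permitted anticoagulant, INR above 1.5, symptom-free ALT/AST of 3–5×ULN, no raised bilirubin. Under assumed frequencies up to 1%, the average effect on 3+3 rejection at a true DLT rate of 20% is at most 1.2 percentage points (15.6 − 14.4). A single case can nonetheless reverse a cohort decision or end a subject's treatment.

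Three stronger inferences are not supported. The stop is not irreversible, because the Sponsor may approve a restart. The step from 1/3 to 2/3 does not apply in every Part 4 cohort as written. Nothing shows that a DLT window was still open at Amendment 6, so the remaining relevance is to any such window and to subjects still on treatment. The change is worth considering, not essential.

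**What to change.** Repeat the Hy's Law bullet's exemption for anticoagulated subjects in stopping criterion 1 (Section 5.6.1.1.15.1) and in DLT liver item 1 (Section 5.2.4.3). Table 30's last row inherits it by reference. Leave all other criteria unchanged.

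Optionally, add a line that ALT/AST of at least 3×ULN with INR above the intended therapeutic range is to be discussed with the Sponsor. The existing 24-hour reporting of Grade 2 or higher elevations makes this a convenience.

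The cost is one existing sentence placed twice, with no extra tests or visits. The downside is the loss of the automatic INR trigger in anticoagulated subjects.

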- Only in those with underlying chronic hepatitis B at study entry (identified by positive hepatitis B surface antigen): quantitative hepatitis B DNA and hepatitis delta antibody. **NOTE:** if hepatitis delta antibody assay cannot be performed, it can be replaced with a PCR of hepatitis D RNA virus (where needed) – as outlined in: <http://www.ncbi.nlm.nih.gov/pmc/articles/PMC1153793/>.

5.6.1.1.15.3 Liver Chemistry Monitoring Criteria

For subjects with ALT $\geq 3 \times \text{ULN}$ **but** $< 8 \times \text{ULN}$ which exhibit a decrease to ALT $\geq 3 \times \text{ULN}$, but $< 5 \times \text{ULN}$ **and** bilirubin $< 2 \times \text{ULN}$, without hepatitis symptoms or rash, and who can be monitored weekly for 4 weeks, the following actions should be taken:

- Notify the Sponsor within 24 hours of learning of the abnormality to discuss subject safety
- Continue study treatment
- Return weekly for repeat liver chemistries (ALT, AST, alkaline phosphatase, bilirubin) until they resolve, stabilize or return to within baseline values

- If at any time the subject meets any of the liver chemistry stopping criteria 1 – 5, proceed as described above
- If, after 4 weeks of monitoring, ALT <3xULN and bilirubin <2xULN, monitor subjects twice monthly until liver chemistries normalize or return to within baseline values.

5.6.1.1.15.4 Drug Restart/Rechallenge Following Liver Events that are Possibly Related to Study Treatment

Approval by Sponsor for study treatment restart can be considered where:

The subject is receiving compelling benefit, benefit of drug restart exceeds risk, and no effective alternative therapy is available. Ethics Committee or Institutional Review Board approval of study treatment restart/rechallenge must be obtained, as required.

If the restart/rechallenge is approved by Sponsor in writing, the subject must be provided with a clear description of the possible benefits and risks of drug administration, including the possibility of recurrent, more severe liver injury or death.

The subject must also provide signed informed consent specifically for the study treatment restart/rechallenge. Documentation of informed consent must be recorded in the study chart.

Study treatment must be administered at the dose specified by Sponsor.

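### For ALT falling through 3-5xULN, section 5.6.1.1.15.3 continues study treatment where Table 30 stops it: every study drug after a peak above 5xULN, pembrolizumab only after a lower peak

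*Combined protocol and SAP*

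**What the plan says.** Section 5.6.1.1.15.3 (Liver Chemistry Monitoring Criteria) applies to ALT of at least 3 and below 8xULN that has come down to at least 3 and below 5xULN, with bilirubin below 2xULN, "without hepatitis symptoms or rash, and who can be monitored weekly for 4 weeks, the following actions should be taken". The listed actions are to notify the Sponsor within 24 hours, "Continue study treatment", and repeat liver tests weekly. If any of stopping criteria 1 to 5 is met, the stopping rules take over.

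Table 30, in the parent section 5.6.1.1.15, sets actions by drug:

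- In the middle band: "Hold pembrolizumab when AST or ALT $>$3.0x to 5.0x ULN". Pembrolizumab resumes at Grade 1 or lower, or at baseline.
- Above that band: "Discontinue pembrolizumab if AST/ALT >5.0x ULN and/or total bilirubin >3.0xULN".
- For the oral drugs: "Hold dabrafenib, and/or trametinib if (any criteria are met". The criteria are AST/ALT above 5xULN, AST/ALT above 3xULN with bilirubin above 2xULN, or bilirubin above 3xULN. Then: "Interrupt dabrafenib and/or trametinib until recovery to Grade ≤1". Failure to recover within 2 weeks means permanent discontinuation.

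Table 10 also withholds pembrolizumab for Grade 2 AST/ALT elevation and refers to Table 30 for Grade 3.

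On restart, section 5.6.1.1.15.1 says of anyone meeting a stopping criterion: "Do not rechallenge with study treatment". Section 5.6.1.1.15.4, on possibly related liver events, begins: "Approval by Sponsor for study treatment restart can be considered where".

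**The concern.** A site that turns to section 5.6.1.1.15.3 and a site that turns to Table 30 can give the same subject opposite treatment while both follow the protocol. Hepatotoxicity is the risk the protocol itself singles out. Section 4.2.1 reports that an earlier immunotherapy plus MAPK-inhibitor trial was discontinued because of it, and section 4.2.2.1 gives it as a reason for the pembrolizumab starting dose.

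The dose-finding data can be affected too. Under section 5.2.4.3, a drug-related toxicity that interrupts any component for more than 21 consecutive days in Cycle 1 and is not controlled within 2 weeks is a DLT. Sections 5.2.4.3 and 8.2.4.2 make DLT evaluability depend on receiving at least 66% of planned treatment over 6 weeks. Whether treatment was held or continued can therefore change how a subject is counted.

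**Working it through.** The plan gives no figure to reproduce, so the check sets the two rules side by side by peak ALT. Throughout, the event is treatment-related, bilirubin is below 2xULN, there are no hepatitis symptoms or rash, weekly monitoring is possible, and ALT is now falling between 3 and 5xULN.

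**Step 1: does recovery to Grade 1 end the conflict?** Table 30 pairs its Grade 2 management with the band above 3 and up to 5xULN, so a subject in that band has not reached Grade 1. Nor is this a return to an eligible baseline, because Table 8 caps AST and ALT at 2.5xULN at entry.

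**Step 2: compare the instructions.**

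| Peak ALT | Section 5.6.1.1.15.3 | Table 30, pembrolizumab | Table 30, dabrafenib/trametinib | Drugs in conflict |
|---|---|---|---|---|
| (a) above 5, below 8xULN | continue | discontinue | interrupt until Grade 1 or lower; permanent stop if not reached in 2 weeks | every study drug received |
| (b) above 3, up to 5xULN | continue | hold until Grade 1 or lower, or baseline | no trigger met | pembrolizumab only |

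In (b) the three oral-drug triggers fail one by one: AST/ALT is not above 5xULN, bilirubin is not above 2xULN, and bilirubin is not above 3xULN. This assumes AST also stays at or below 5xULN, since section 5.6.1.1.15.3 names only ALT and Table 30 names either.

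**Step 3: test with two subjects.**

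- ALT 6xULN, then 4xULN a week later. Entry to 5.6.1.1.15.3: 3 ≤ 6 < 8 and 3 ≤ 4 < 5, both met. No stopping criterion applies: bilirubin is low, 6 is below 8, the value at or above 5 did not last 2 weeks, there are no symptoms, and weekly monitoring is possible. Section 5.6.1.1.15.3 continues treatment. In Table 30, 6 > 5, so pembrolizumab is discontinued and the oral drugs stay off at 4xULN.
- ALT 4.8xULN, then 3.5xULN. Section 5.6.1.1.15.3 continues treatment. Table 30 holds pembrolizumab and leaves the oral drugs running.

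**Step 4: size over the monitoring period.** 4 weeks × 7 = 28 days. With a 21-day infusion interval, 28/21 = 1.33, so one or two infusions fall inside. In (a) up to 28 days of oral dosing also differ (fewer for intermittent trametinib), and pembrolizumab differs beyond the 4 weeks because Table 30 discontinues it. In (b) only the infusions differ.

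**Step 5: restart.** A subject with a possibly related event who meets a stopping criterion fits both the prohibition in 5.6.1.1.15.1 and the title of 5.6.1.1.15.4. Neither section refers to the other.

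The label on Table 30's first row, as I read it, gives AST or ALT at or above 5.0xULN, which does not match that row's actions. This may be a text-extraction fault, and nothing here relies on it.

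**The case against.** Five points can be made on the other side.

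- **Relatedness.** Section 5.6.1 applies the treatment guidelines to events judged related to study treatment. For an unrelated elevation the Table 30 actions need not apply. This stands, and the point is limited to related events.
- **Which text governs.** Section 5.6.1.1.15 names Tables 10 and 30 as the source of hepatic dose modification, and 5.6.1.1.15.3 is headed as monitoring. That suggests an intention. But 5.6.1.1.15.3 contains a dosing instruction, and nothing makes it subordinate to the tables.
- **Flexible definition.** Section 5.2 lets the term for study treatment mean one drug or several. In group (a), however, Table 30 leaves no drug to continue, and in group (b) 5.6.1.1.15.3 does not except pembrolizumab.
- **Sponsor notification.** Each case reaches the Sponsor within 24 hours. This limits harm in practice but does not say which instruction applies.
- **Restart.** Section 5.6.1.1.15.4 requires written Sponsor approval, ethics approval as required, compelling benefit, no effective alternative and specific signed consent. It can fairly be read as a gated exception to a default, or as covering only events short of the stopping criteria. A reader might infer a flat contradiction; the text supports only a missing cross-reference.

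**Conclusion.** The contradiction is real for treatment-related elevations. It covers every study drug the subject receives after a peak above 5 and below 8xULN, and pembrolizumab alone after a peak above 3 and up to 5xULN.

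Two stronger readings are tempting and are not supported. One is that all three drugs conflict after any peak below 8xULN; step 2 shows that dabrafenib and trametinib continue under both rules when the peak is 5xULN or less. The other is that the Part 3 adverse-event comparisons are compromised. Sections 5.2.5 and 7.1.5.3 report the Part 3 final analysis as done, so new wording cannot change it. Part 3 was double-blind with the same rules in both arms, and nothing in the documents shows that they were applied differently between arms.

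The prospective relevance is to Part 3 subjects who stay on treatment under the same toxicity guidelines (section 8.2.1) and to subjects in Parts 4 and 5. The DLT consequence arises only for subjects still within a DLT observation period. The documents give no count of affected subjects. The restart issue is a secondary clarification.

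**What to change.** Reconcile section 5.6.1.1.15.3 with Tables 10 and 30 so that a single instruction applies in the falling 3-5xULN range. State for each drug, and for each peak band, whether it is continued, held or discontinued, and name the drugs instead of using the general term. Align the 2-week recovery limit in Table 30 with the 4-week monitoring period. The sponsor decides which rule stands; this review takes no view.

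Secondarily, cross-reference sections 5.6.1.1.15.1 and 5.6.1.1.15.4 and state whether subjects who met any of stopping criteria 1 to 5 can enter the restart/rechallenge pathway.

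The cost is amendment wording and site notification. The reconciliation itself requires no new tests or visits.
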